6.14.6.2. Eosinophilia and Eosinophil-Related Disorders

In addition to the standard laboratory analysis (Section 6.14.3), eosinophilia and eosinophil-related AE will be summarized. Details regarding eosinophil-related PTs are in Compound Level Safety Standard.

Table KGAB.6.18. Summary Tables Related to Eosinophilia and Eosinophil-Related AE

Analysis	Population
Shift table summarizing the number and percentage of participants within each maximum baseline category versus each maximum postbaseline category by treatment	S, A
Summary of eosinophilia and eosinophil-related TEAE by PT	S, A

Abbreviations: A = All Lebrikizumab Safety Population; AE = adverse event; PT = Preferred Term; S = Safety Population; TEAE = treatment-emergent adverse event.

6.14.6.3. Infections, Including Herpes Infections and Relevant Parasitic Infections

Infections will be defined using the PTs from the MedDRA Infections and Infestations SOC. The MedDRA terms used to identify infections considered to be opportunistic infections (OI) in patients with immune mediated inflammatory conditions treated with immunomodulatory drugs are based on Winthrop et al. (2015) and are listed in the compound level safety standards. The list contains narrow (more specific) and broad (less specific) PTs with respect to these prospectively defined OIs. Definitions of herpes infections, parasitic infections and skin infections are listed in the compound level safety standards.

Table KGAB.6.19. Summary Tables/Listing Related to Infection Related AE

Analysis	Population
Summary of treatment-emergent infections by PT by maximum severity	S, A
Summary of serious infections by PT	S, A
Summary of infection AEs resulting in permanent study drug discontinuation	S, A
Treatment-emergent potential OI by PT nested with categories for narrow terms and broad terms separately	S, A
Treatment-emergent adverse events, herpes and parasitic infections	S, A
Treatment-emergent adverse events, skin infection	S, A
Summary and/or listing of Infection follow-up form	S
A listing of patients with potential OI, Serious Infection, herpes and parasitic infections	S

Abbreviations: A = All Lebrizumab Safety Population; AE = adverse event; OI = opportunistic infections; PT = Preferred Term; S = Safety Population.

6.14.6.4. Conjunctivitis

Conjunctivitis are events of special interest and will be identified using PTs nested within the categories of conjunctivitis and Keratitis as described in the Compound Level Safety Standards:

Table KGAB.6.20. Summary Tables/Listing Related to Conjunctivitis

Analysis	Population
Summary of TEAE of conjunctivitis within categories	S, A
Summary and/or listing of conjunctivitis and eye inflammation follow-up form	S
A listing of patients with conjunctivitis	S

Abbreviations: A = All Lebrizumab Safety Population; S = Safety Population; TEAE = treatment-emergent adverse event.

6.14.6.5. Hypersensitivity

Potential hypersensitivity reactions will be determined using the following SMQs: anaphylactic reaction, hypersensitivity, and angioedema. Potential hypersensitivity will be categorized as immediate (i.e., occurring the same day as drug administration) and non-immediate (i.e., occurring after the day of study drug administration but prior to subsequent drug administration). The planned summaries are provided in [Table KGAB.6.21](#).

Table KGAB.6.21. Summary Tables Related to Hypersensitivity

Analysis	Population
for immediate hypersensitivity: (1) combined narrow/algorithmic search (that is, any narrow term from any one of the SMQs, or anaphylaxis algorithm); (2) narrow search (that is, any narrow term) by SMQ; (3) broad search (that is, any narrow or broad term) by SMQ; and (4) TEAEs (occurring on the day of study drug administration) by PT not in any of the 3 SMQs	S, A
for nonimmediate hypersensitivity: (1) combined narrow search (that is, any narrow term from any one of the SMQs); (2) narrow search (that is, any narrow term) by SMQ; and (3) broad search (that is, any narrow or broad term) by SMQ	S, A

Abbreviations: A = All Lebrikizumab Safety Population; MedDRA = Medical Dictionary for Regulatory Activities; PT = Preferred Term; S = Safety Population; SMQ = Standardised MedDRA Query; TEAE = treatment-emergent adverse events.

6.14.6.6. Injection Site Reactions (ISR)

Injection site reactions (ISRs) are AEs localized to the immediate site of the administration of a drug. The evaluation of study drug related ISRs will be through the unsolicited reporting of ISR TEAEs. Injection site reactions will be defined using the MedDRA High Level Term (HLT) of Injection Site Reaction, excluding certain PTs related to joints as described in the Compound Level Safety Standards.

Table KGAB.6.22. Summary Tables Related to Injection Site Reactions

Analysis	Population
Summary of TEAE of ISR overall and by PT	S, A

Abbreviations: A = All Lebrikizumab Safety Population; HLT = High Level Term; ISR = injection site reaction; PT = Preferred Term; TEAE = treatment-emergent adverse event; S = Safety Population.

6.14.6.7. Malignancies

Malignancies will be defined using PTs from the Malignant tumors SMQ and summarized separately for the 2 categories: Non-melanoma skin cancer (NMSC) and Malignancies excluding NMSC as below.

Table KGAB.6.23. Summary Tables Related to Malignancies

Analysis	Population
Summary of TEAE of malignancies within categories of NMSC and malignancy excluding NMSC	S, A

Abbreviations: A = All Lebrikizumab Safety Population; NMSC = non-melanoma skin cancer; TEAE = treatment-emergent adverse event; S = Safety Population.

6.14.6.8. Atopic Dermatitis Exacerbation

Atopic dermatitis exacerbation will be defined using PTs specified in the Compound Level Safety Standards and summarized below:

Table KGAB.6.24. Summary Tables Related to Atopic Dermatitis Exacerbation

Analysis	Population
Summary of TEAE of atopic dermatitis exacerbation	S, A

Abbreviations: A = All Lebrikizumab Safety Population; TEAE = treatment-emergent adverse event; S = Safety Population.

6.14.6.9. Suicide/Self-Injury Standardised Medical Dictionary For Regulatory Activities Query

Suicide/self-injury will be defined as described in the Compound Level Safety Standards and summarized below.

Table KGAB.6.25. Summary Tables Related to Suicide/self-injury Standardised Medical Dictionary For Regulatory Activities Query

Analysis	Population
Summary of TEAE of Suicide/self-injury SMQ	S, A

Abbreviations: A = All Lebrikizumab Safety Population; MedDRA = Medical Dictionary for Regulatory Activities; TEAE = treatment-emergent adverse event; S = Safety Population; SMQ = Standardised MedDRA Query.

6.15. Subgroup Analyses

6.15.1. Efficacy Subgroup Analyses

Subgroup analyses will be conducted for the primary endpoints IGA 0/1, EASI-75, EASI-90 and 4-point improvement in Pruritus NRS at Week 16 in the ITT Population using MCMC-MI approach as in primary analysis (Section 6.4.1.1). A logistic regression analysis with treatment, subgroup, and treatment-by-subgroup interaction as factors will be used. The treatment-by-subgroup interaction will be tested using the Firth correction (Firth 1993) at the 10% significance level. Treatment group differences will be evaluated within each subgroup using the chi-square test, regardless of whether the interaction is statistically significant. If any group within the subgroup (for example, yes, no) is <10% of the total population, only descriptive statistics will be provided for that subgroup (that is, no inferential testing).

Forest plots may be created to illustrate the treatment differences with 95% CIs between each of the lebrikizumab treatment groups and placebo group, by each subgroup category.

The following subgroups will be analyzed:

- Age group (Adolescents (12 to <18), Adults ≥ 18)
- Age group (Adolescents (12 to <18), Adults ≥ 18 to < 65, ≥ 65 to < 75, ≥ 75)
- Sex (male, female)
- Race (American Indian or Alaska Native, Asian, Black or African American, Native Hawaiian or Other Pacific Islander, White, Multiple, Other, Not Reported)
- Ethnicity (Hispanic or Latino, Not Hispanic or Latino, Not reported, Unknown)

- Region (as defined in Section 6.5)
- Weight category (<60 kg, ≥60 to <100 kg, ≥100 kg)
- BMI category (Underweight (<18.5 kg/m²), Normal (≥18.5 and <25 kg/m²), Overweight (≥25 and <30 kg/m²), Obese (≥30 and <40 kg/m²), Extreme obese (≥40 kg/m²))
- Duration since AD onset category (0 to <2 years, 2 to <5 years, 5 to <10 years, 10 to <20 years, ≥20 years)
- Baseline IGA 3 versus 4
- Baseline pruritus <4 versus ≥4
- Prior use of systemic treatment (yes, no)

Some additional subgroup analyses may be added to meet regulatory requirement. The analysis of additional subgroups will not require an amendment to the SAP.

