### **8.2.5. Pruritus**

Pruritus will be assessed by the patient using a Pruritus Numerical Rating Scale (NRS). The Pruritus NRS is an 11-point scale used by patients to rate their worst itch severity over the past 24 hours with 0 indicating “No itch” and 10 indicating “Worst itch imaginable.” Assessments will be recorded daily by the patient using an electronic diary. Data will be transferred to the clinical database.

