### 9.5.5. Subgroup Analyses

Subgroup analyses will be conducted for the ITT populations for the following subgroups: Adolescents (Age 12 to <18 years) vs. Adults (Age  $\geq 18$  years), sex, race, baseline IGA score (3 or 4), region (US, Europe, Rest of the World). Subgroup analysis will be conducted on the

primary endpoint of IGA (0,1), EASI-75, EASI-90 and percent of patients with pruritus improvement  $\geq 4$  points, all at Week 16.

Sensitivity analyses will be addressed in a full statistical analysis plan.

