6.6. Multiple Comparisons/Multiplicity

6.6.1. Multiplicity Control for FDA

A prespecified graphical multiple testing approach (Bretz et al. 2009, 2011) will be implemented to control the overall Type I error rate at two-sided alpha of 0.05, for all primary and major secondary endpoints for FDA. Multiple testing adjusted p-values using “Algorithm 2” described by Bretz et al. (2009) will be calculated, and any hypothesis tests with a multiple testing adjusted p-value of less than 0.05 will be considered statistically significant. This graphical approach is a closed testing procedure; hence, it strongly controls the family-wise error rate across all endpoints (Bretz et al. 2009, 2011; Alosch et al. 2014). Each hypothesis is represented as a node in a graph. Directed arrows between the nodes with associated weights represent how alpha is passed from its initial allocation to other nodes.

The following is a list of primary and major secondary endpoints to be tested for FDA.

Primary endpoint:

- [IGA01 W16] Percentage of patients with an Investigator Global Assessment (IGA) score of 0 or 1 and a reduction ≥ 2 points from Baseline to Week 16.

Major secondary endpoints:

- [EASI-75 W16] Percentage of patients achieving EASI-75 ($\geq 75\%$ reduction from Baseline in Eczema Area and Severity Index [EASI] score) at Week 16.
- [EASI-90 W16] Percentage of patients achieving EASI-90 ($\geq 90\%$ reduction from Baseline in EASI score) at Week 16.
- [Pruritus NRS-4 W16] Percentage of patients with a Pruritus Numerical Rating Scale (NRS) of ≥ 4 -points at Baseline who achieve a ≥ 4 -point reduction from Baseline to Week 16.
- [Pruritus NRS-4 W4] Percentage of patients with a Pruritus NRS of ≥ 4 -points at Baseline who achieve a ≥ 4 -point reduction from Baseline to Week 4.
- [Pruritus NRS-4 W2] Percentage of patients with a Pruritus NRS of ≥ 4 -points at Baseline who achieve a ≥ 4 -point reduction from Baseline to Week 2.
- [IGA01 W4] Percentage of patients with an IGA score of 0 or 1 and a reduction ≥ 2 points at Week 4.

- [IGA01 Adult W16] Percentage of patients with an IGA score of 0 or 1 and a reduction ≥ 2 points at Week 16 in adults.
- [Sleep loss W16] Percentage of patients with a Sleep-loss score ≥ 2 points at Baseline who achieve a ≥ 2 points reduction from Baseline at Week 16.

Figure KGAB.6.2 describes the graphical testing scheme for FDA.

[figure not shown]

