SCORAD90	% Improvement in SCORAD from baseline $\geq 90\%$: % change from baseline ≤ -90	Missing if baseline or observed value is missing.		

	
 Subjective assessment of itch and of sleeplessness is recorded for each symptom by the patient or relative on a VAS, where 0 is no itch (or sleeplessness) and 10 is the worst imaginable itch (or sleeplessness), with a maximum possible score of 20 (assigned as “C” in the overall SCORAD calculation. 			
Pruritus Numeric Rating Scale (NRS)	The Pruritus Numeric Rating Scale (NRS) is a an 11-point scale used by patients to rate their worst itch severity over the past 24 hours with 0 indicating “No itch” and 10 indicating “Worst itch imaginable.” Assessments will be recorded daily by the patient using an electronic diary.	Pruritus NRS prorated weekly mean score	The prorated weekly mean is based on previous 7 days. If the patient has at least one daily score, the weekly mean is the prorated average of daily scores within the given week. Single item; range 0-10. eDiary data are mapped to study visit per Appendix 1 .	Weekly mean score missing if the patient has no Pruritus-NRS responses within the week.
		Change from baseline in Pruritus NRS prorated weekly mean score Percent change from baseline in Pruritus NRS prorated weekly mean score	Change from baseline: observed Pruritus prorated weekly mean score – baseline Pruritus weekly mean score % change from baseline: $100 \times \frac{\text{Observed score} - \text{Baseline}}{\text{Baseline}}$	Missing if baseline or observed value is missing.
		4-point Pruritus improvement in Pruritus NRS prorated weekly mean score	Change from baseline in Pruritus NRS prorated weekly mean score ≤ -4	Missing if baseline is missing or observed value is missing.

Sleep-loss due to pruritus	Sleep-loss due to pruritus will be assessed by the patient. Patients rate their sleep based on a 5-point Likert scale [0 (not at all) to 4 (unable to sleep at all)]. Assessments will be recorded daily by the patient using an electronic diary.	Sleep-loss prorated weekly mean score	The prorated weekly mean is based on previous 7 days. If the patient has at least one daily score within the week, the weekly mean is the prorated average of daily scores within the given week. Single item; range 0 to 4. eDiary data are mapped to study visit per Appendix 1 .	Weekly mean score missing if the patient has no Sleep-loss responses within the week.

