	Proportion of patients with EASI-75 after lebrikizumab retreatment	NA	Descriptive statistics	Maintenance W24-48 Escape Population	No comparisons. Every 4 weeks after escape and re-treated by lebrikizumab 250 mg Q2W	Secondary analysis
Body Surface Area (BSA) Affected by AD	Change from baseline in BSA score	Supportive Estimand (Hypothetical)	MMRM with observed data	ITT	Leb 250 mg Q2W vs PBO; Week 16 and all scheduled visits in Induction Period	Secondary analysis

Measure	Variable	Estimand (Section 6.2)	Analysis Method (Section 6.1)	Population (Section 6.1.1)	Comparison/Time Point	Analysis Type
		Maintenance Supportive Estimand (Hypothetical)	ANCOVA with LOCF	Maintenance Primary Population	Leb 250 mg Q2W vs PBO; Leb 250 mg Q4W vs PBO; all scheduled visits in Maintenance Period	Secondary analysis
		NA	Descriptive statistics	Maintenance W16 Escape Population	No comparisons. all scheduled visits in Maintenance Period	Secondary analysis
Pruritus Numeric Rating Scale (NRS)	Change from baseline in Pruritus NRS Percent Change from baseline in Pruritus NRS	Primary Estimand (Hybrid)	ANCOVA with MCMC-MI	ITT	Leb 250 mg Q2W vs PBO; Week 16 and all scheduled visits in Induction Period	Key secondary analysis: W16; Secondary analysis: other timepoints
		Supportive Estimand (Hypothetical)	MMRM with observed data	ITT	Leb 250 mg Q2W vs PBO; Week 16 and all scheduled visits in Induction Period	Supplementary analysis
		Maintenance Primary Estimand (Hybrid)	ANCOVA with MCMC-MI	Maintenance Primary Population	Leb 250 mg Q2W vs PBO; Leb 250 mg Q4W vs PBO;	Secondary analysis
		Maintenance Supportive Estimand (Hybrid)	ANCOVA with MCMC-MI			Supplementary analysis
		Maintenance Supportive Estimand (Hypothetical)	ANCOVA with LOCF			Supplementary analysis
		NA	Descriptive statistics	Maintenance W16 Escape Population	No comparisons. all scheduled visits in Maintenance Period	Secondary analysis

Measure	Variable	Estimand (Section 6.2)	Analysis Method (Section 6.1)	Population (Section 6.1.1)	Comparison/Time Point	Analysis Type
	Proportion of patients achieving at least 4-point improvement in pruritus NRS	Primary Estimand (Hybrid)	CMH analysis with MCMC-MI	ITT, ITT with Baseline Pruritus NRS score at least 4, ITT with Baseline Pruritus NRS score at least 5	Leb 250 mg Q2W vs PBO; Week 16 and all scheduled visits in Induction Period	Key secondary analysis: 2, 4, and 16 for ITT with Baseline Pruritus NRS score at least 4. Secondary analysis: other timepoints and population

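### SAP 6.15.1 applies the baseline-itch subgroup factor to the 4-point itch response in full ITT, although no patient below 4 can have an observed response

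*SAP*

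**What the plan says.** SAP 6.15.1 names four Week 16 endpoints for subgroup analysis: IGA 0/1, EASI-75, EASI-90 and the itch response, the last given as "4-point improvement in Pruritus NRS at Week 16 in the ITT Population using MCMC-MI approach as in primary analysis". It states no baseline itch threshold. One factor list serves all four endpoints and includes "Baseline pruritus <4 versus ≥4". On testing, the section says: "Treatment group differences will be evaluated within each subgroup using the chi-square test, regardless of whether the interaction is statistically significant". Interaction is tested by logistic regression with the Firth correction at the 10% level. A category holding under 10% of the total population gets descriptive statistics only.

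Protocol 9.5.5 is equally unrestricted. It applies the subgroups to ITT and describes the endpoint as "percent of patients with pruritus improvement" of at least 4 points. SAP Table KGAB.6.11 defines response as "Change from baseline in Pruritus NRS prorated weekly mean score ≤ -4", again without a threshold.

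The multiplicity-controlled endpoint is different. For the Week 16 assessment, SAP 6.6.1 gives it as "Percentage of patients with a Pruritus Numerical Rating Scale (NRS) of ≥ 4 -points at Baseline who achieve a ≥ 4 -point reduction from Baseline". Table KGAB.6.12 lists three separate populations for the responder analysis, "ITT, ITT with Baseline Pruritus NRS score at least 4, ITT with Baseline Pruritus NRS score at least 5", and assigns the key secondary, tipping-point and non-responder-imputation analyses to the one with baseline at least 4.

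**The concern.** A fall of 4 points needs a starting value of at least 4. Nothing in Protocol 4.1 sets a minimum itch score; the only itch-related entry criterion is diary completion. The SAP's baseline tables also report itch below 4 and at least 4 as separate categories, so the plan expects that patients below 4 may be enrolled.

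Two consequences follow. Applied to this endpoint, the baseline-itch factor compares a level where response is possible with one where it is not, and a reader could take the contrast for effect modification. For every other factor, patients who cannot respond stay in the denominator of both arms, so the displayed effect is not the one estimated for the key secondary endpoint.

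**Working it through.** The plan gives no figure on this point to reproduce. The inputs are as follows.

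- Scale: daily scores run from 0 (itch absent) to 10 (worst), per Protocol 8.2.5.
- Response: change of -4 or lower (SAP Table KGAB.6.11).
- Population: all randomized patients, about 400, allocated 2:1 (SAP 5.2 and Table KGAB.6.1).
- Imputation: SAP 6.4.1.1 uses a multivariate normal model, does not round itch values and states no bound at 0. Values after rescue or discontinuation for lack of efficacy are set to baseline.
- Not in the documents, so assumed: the share f of a subgroup with baseline below 4 (5% to 40%), and response rates among patients at 4 or above (45% vs 12%; also 40% vs 10% and 50% vs 20%).

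**1. The lower level of the itch factor.** The largest possible fall equals the baseline value, so a baseline of 3.9 allows at most 3.9. Patients set to baseline have change 0. Observed response is therefore 0% in both arms. The expected number of responders per arm is (arm size × 0)/total = 0, so the chi-square statistic is 0/0.

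If the threshold of 4 is instead read into the endpoint, the lower level contains no patients. The factor is unusable for this endpoint on either reading.

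**2. Imputed responders.** For baseline b, conditional mean m and SD s, the chance of an imputed response is Φ((b − 4 − m)/s). With b = 3.5, m = 2.5 and s = 1, this is Φ(−3.0) = 0.1%. With m = 1 and s = 2, it is Φ(−0.75) = 22.7%. The values of m and s are assumptions. Any such response requires a score below 0.

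**3. The interaction for that factor.** The 10% rule applies below 0.10 × 400 = 40 patients. Suppose exactly 40 patients are below 4, split 27:13, with no responders. The model with treatment, a two-level factor and their interaction is saturated, so the Firth correction adds 0.5 to each cell. The odds ratio at the lower level is (0.5/27.5)/(0.5/13.5) = 13.5/27.5 = 0.49. Its log has a standard error of √(1/0.5 + 1/27.5 + 1/0.5 + 1/13.5) = 2.03. The value falls below 1 only because allocation is 2:1.

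**4. Risk differences for other factors.** With the same f in both arms, the ITT difference is (1 − f) × the difference among patients at 4 or above. At 45% vs 12% the latter is 33 points:

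| f | ITT rates | Difference (points) | Odds ratio |
|---|---|---|---|
| 0 | 45.0% vs 12.0% | 33.0 | 6.00 |
| 5% | 42.75% vs 11.4% | 31.4 | 5.80 |
| 10% | 40.5% vs 10.8% | 29.7 | 5.62 |
| 20% | 36.0% vs 9.6% | 26.4 | 5.30 |
| 30% | 31.5% vs 8.4% | 23.1 | 5.01 |

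Two levels with the same true effect and shares of 5% and 20% differ by 33 × 0.15 = 5.0 points. For a subgroup of 133 vs 67 patients at f = 5%, the 95% half-width is 1.96 × √(0.4275 × 0.5725/133 + 0.114 × 0.886/67) = 11.3 points. Over the three rate pairs and both shares it is about 10 to 13 points.

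**5. The logistic interaction test for other factors.** Take two levels of 133/67, with f = 5% and 20%. The log odds ratios differ by ln(5.80/5.30), about 0.091. Summing 1/(np(1 − p)) over the four arms and taking the square root gives a standard error of 0.619. The rejection rate at the 10% level is Φ(−1.645 + 0.147) + Φ(−1.645 − 0.147) = 10.4%. The same calculation gives 10.2% for 40% vs 10% and 10.6% for 50% vs 20%. For an extreme contrast of 5% vs 40%, the three rate pairs give 10.9% to 12.3%.

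**The case against.** The strongest reply is that full ITT is a legitimate population for this response. Protocol 2.3 and SAP Table KGAB.4.1 list a 4-point itch change by visit, with no baseline threshold, among the other secondary endpoints, and Table KGAB.6.12 names plain ITT for the responder analysis. Nothing in 6.15.1 says its subgroups must mirror the key secondary endpoint. This stands: the mismatch with the key secondary is a reason to align the two, not proof of error.

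The text may also be shorthand. Section 6.15.1 points to 6.4.1.1, where the itch responses are defined for patients at 4 or above. The tipping-point section uses similarly loose wording, which Table KGAB.6.12 resolves to that population. However, 6.15.1 says ITT, and the table has no subgroup row to settle it. The shorthand reading also leaves the lower level of the itch factor with no patients.

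A reader might infer that every subgroup result is unevenly diluted and that the interaction tests will report eligibility as effect modification. The documents do not support that. They give no share below 4, overall or by subgroup, so uneven dilution is certain only for the itch factor. Patients who cannot respond are non-responders in both arms, so a null effect stays null and direction is preserved. On the log-odds scale that the SAP uses, the distortion nearly vanishes. Power is barely affected: at f = 20%, a 133/67 subgroup has 99.2% in ITT and 99.6% when restricted, at 45% vs 12%.

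Finally, a row of 0% versus 0% is visibly uninformative, and the 10% rule may suppress its test. Both points limit the harm, but neither makes the planned analysis meaningful.

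**Conclusion.** The point holds in limited form. The baseline-itch factor cannot be used with the 4-point itch response. That follows from the scale floor and the SAP's own definitions, with no assumption about the data. Whether the undefined test is reached depends on at least about 40 of 400 patients starting below 4, which the documents do not tell us.

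For other factors the effect is conditional and small. Forest-plot differences could shift by a few points if the share below 4 differs between levels, and the logistic interaction test is practically unaffected under the assumed rates. The broader inference that this plan produces false subgroup findings across factors is not supported.

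These are exploratory displays. The primary, co-primary and multiplicity-controlled analyses are untouched.

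**What to change.** In SAP 6.15.1, state that the 4-point Pruritus NRS subgroup analyses use the ITT patients with baseline score at least 4, a population already named in Table KGAB.6.12. Omit the baseline-itch factor for this endpoint only, and keep it for IGA 0/1, EASI-75 and EASI-90.

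The cost is one sentence and a programming filter, with no new data and no patient burden. Because SAP Version 4 was approved after the study team was unblinded to induction treatment, the change should be labelled as made after that unblinding. Since Protocol 9.5.5 also specifies ITT, the clinical study report should record the change and its reason, as SAP 6.1 provides. If the full-ITT version is wanted as well, it can be shown as a labelled supplement.
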